6.3. Randomisation	12
6.4. Trial intervention	12
Intervention arm.....	12
Control arm	13
6.5. Data collection and collation	13
Dataset	13
6.6. Predefined protocol violation	14
6.7. Follow up procedures	14
6.8. Schedule of assessment	14
7. Statistical considerations	15
7.1. Sample size calculation	15
TABLE 1: Sample size calculations for the ASOS-2 Trial based on a power of 80%, 2-sided $\alpha = 0.05$ and a mean cluster size of 100 patients	15
7.2. Statistical analysis	16
7.3. Subgroup analyses	Error! Bookmark not defined.
7.4. Secondary studies	16
8. Research ethics	18

8.1 Ethical principles	18
9. Data handling and record keeping.....	19
10. Monitoring and auditing	20
10.1 Training of investigators	20
11. Trial management and committees.....	21
11.1 Trial management group.....	21
11.2 Trial Steering Committee	21
11.3 Data and Safety Monitoring Board	21
12. Data management and ownership	22
13. Publication plan and public communication of trial results	23
References	24
Appendix 1	25
African Surgical OutcomeS-2 (ASOS-2) Trial: Definitions document	25
Appendix 2	37
African Surgical OutcomeS-2 (ASOS-2) Trial: Hospital ‘broadcasting’ signage	37
Appendix 3	38
African Surgical OutcomeS-2 (ASOS-2) Trial: Case Record Form (CRF) (Control arm).....	38
African Surgical OutcomeS-2 (ASOS-2) Trial: Case Record Form (CRF) (Intervention arm).....	39
Appendix 4	40
ASOS-2 Surgical Risk Calculator Score Card	40
Appendix 5	41
‘Increased postoperative surveillance’ bedside guide.....	41

1. List of abbreviations

ASOS	African Surgical Outcomes Study
EuSOS	European Surgical Outcomes Study
ISOS	International Surgical Outcomes Study

2. Summary

Short title	ASOS-2 Trial
Methodology	An international, multicentre, African cluster randomised trial
Research sites	Hospitals undertaking adult surgery in participating countries.
Objectives	To determine whether increased postoperative surveillance in high-risk adult surgical patients reduces overall in-hospital mortality in surgical patients aged 18 years and over in Africa.
Number of patients	664 hospital clusters with a recruitment target of 100 patients per site (approximately 66,400 patients)
Inclusion criteria	All consecutive adult patients aged 18 years and over admitted to participating centres undergoing elective and non-elective surgery
Statistical analysis	The primary outcome measure is in-hospital mortality censored at 30 days of randomisation. The analysis will be conducted according to intention-to-treat principles; all participants with a recorded outcome will be analysed according to the treatment group to which they were randomised.
Recruitment start date	May 2019
Recruitment end date	March 2020
Trial duration	Until hospital discharge, censored at 30 days

3. Introduction

The non-cardiac surgical population represents a major global public health burden with approximately 234 million major surgical procedures performed worldwide each year.¹ In unselected non-cardiac surgical patients, reports of early postoperative mortality vary between 2 and 4%,^{2,3} with an annual global mortality of 5 to 10 million. Surgery is a cost-effective intervention,⁴ even in low to middle income countries⁵ and as such it is considered a core component of health.⁶ The Lancet Commission on Global Surgery was established to define safe surgery and develop strategies to ensure the adequate provision of safe surgery.⁷

Recently, the African Surgical Outcomes Study (ASOS) demonstrated, that despite a patient low risk profile and low complication rates, patients in Africa were twice as likely to die following surgery when compared to the global average.⁸ ASOS provides the most comprehensive data on surgical outcomes in Africa, comprising 25 countries, 247 hospitals, and data from over 11 000 patients.⁸ Importantly, 95% of the deaths in ASOS occurred in the postoperative period, suggesting that many lives could be saved by effective surveillance for physiological deterioration amongst the patients who developed complications.⁸ In ASOS, the median number of combined anaesthesia, surgical and obstetric specialists was 0.7 (IQR 0.2-1.9) per 100,000 population,⁸ which is well below the documented inflection point of 20 to 40 specialists per 100,000 population necessary to significantly decrease surgical mortality.⁷

It is likely that a major contributor to the high mortality in ASOS was 'failure to rescue' after a postoperative complication partly due to an inadequacy of sufficient human resources necessary to identify postoperative surgical patients at risk. A potential solution to improving surgical outcomes in Africa is identification of the high-risk surgical patient prior to further physiological deterioration.

The objective of this trial is to assess whether increased postoperative surveillance of surgical patients at increased risk of postoperative morbidity or mortality is associated with improved survival.

4. Trial objectives

4.1 Primary objective

To determine whether increased postoperative surveillance in high-risk adult surgical patients reduces overall in-hospital mortality in adult surgical patients aged 18 years and over in Africa.

4.2 Primary outcome measure

In-hospital mortality, censored at 30 days if the patient is still alive and in-hospital.

4.3 Secondary objective

To determine whether increased postoperative surveillance in high-risk adult surgical patients reduces the overall incidence of the composite of severe in-hospital complications and mortality in adult surgical patients aged 18 years and over in Africa.

4.4 Secondary outcome measure

Composite of severe in-hospital complications and mortality, censored at 30 days if the patient is still alive and in-hospital.

A full list of definitions is available in the 'Definitions document' in appendix 1.

5. Methodology

5.1 Study design

ASOS-2 is an African, international, multicentre, cluster randomised trial.

5.2 Inclusion criteria

[figure not shown]
- Patients
 - All consecutive adult patients aged 18 years and over admitted to participating centres undergoing elective and non-elective surgery
- Participating surgical centres
 - Randomised according to a stratification based upon the level of the surgical facility and the surgical case load. Recruitment will run until March 2020.

We plan to randomise 664 hospitals to either increased postoperative surveillance or standard care for high-risk adult (≥ 18 years) surgical patients. The follow up is in-hospital. This study will be registered on ClinicalTrials.gov.

5.3 Exclusion criteria

- Prior participation in ASOS-2

5.4 Study flow diagram

6. Trial procedures

6.1 Recruitment and screening

This is a pragmatic trial. It is an African, international cluster randomised controlled trial in several African countries. Participating surgical sites will be randomised to either increased postoperative surveillance or usual postoperative care. We expect all consecutive adult patients aged 18 years and over admitted to participating centres undergoing elective and non-elective surgery to be included in the trial. 'Broadcasting' through appropriate hospital notices and signage will inform the patients and the public that the hospital is participating in the cluster randomised trial.

6.2 Informed consent and trial participation

The requirement for informed patient consent is expected to vary according to regulations of the participating nations. The national leaders will ensure ethics approval is obtained from their respective countries and centres prior to participation.

We will apply to all ethics committees for a waiver of consent for participating trial sites for the following reasons. Firstly, more than 50% of surgery in Africa is urgent or emergent, and urgent or emergent surgery is a strong independent predictor of postoperative mortality in Africa.⁸ Attempts to obtain traditional consent in the preoperative period in predominantly urgent and emergent surgery, which may include patients with a decreased level of consciousness may lead to non-consecutive patient enrolment in the ASOS-2 Trial. It is likely that this would lead to a biased sample, with artificially low estimates of adverse outcomes in African surgical patients, and data following the trial which are not generalisable to the majority of African surgical patients. Secondly, for these reasons, a waiver of consent is increasingly common around the world in both interventional and observational research involving time-sensitive procedures, such as surgery. Thirdly, generating biased and poorly generalizable data would not address the research question, and thus would dishonour the contributions of the other included patients, and would be wasteful research, in a resource-limited environment. Fourthly, we believe that the trial intervention is low risk. Furthermore, the patients in the control arm will receive the current standard postoperative care. The intervention group will receive a low risk intervention which is only aimed at increasing surveillance of at-risk patients. Finally, we would use 'broadcasting' at participating sites to ensure that all patients and family members were aware that the surgical site was a participating surgical trial site, through appropriate signage (appendix 2).

6.3. Randomisation

Participating sites will be randomised to normal postoperative care (“SOC”), or increased postoperative surveillance (“Intervention”) in four recruitment blocks (calendar time blocks). Randomisation in each block will be stratified by country and by level of the surgical facility with a fixed block size of 2. The randomisation algorithm will seek to balance randomisation arms by simulating randomisations with an automated filter to screen out poorly balanced randomisations. In the second and subsequent recruitment blocks, the randomisation algorithm will use knowledge of the previous randomisations and a similar simulation and filtering approach to ensure reasonable balance across arms and across level of surgical facility. This approach was developed on the basis of a simulation model for the randomisation that was used to evaluate the probability of overall balance of randomisation arms and balance within level of care strata if randomising recruitment phases in waves. Results of 10,000 simulation runs indicated that a balanced simulation within the bounds described below would be obtained >50% of the time without the filtering step.

The algorithm is described briefly here:

For recruitment phase 1:

1. Simulate stratified block randomisation within country and level of facility
2. Check that simulated randomisation has percent SOC between [48% - 52%]
3. If NO, then repeat steps 1 and 2. If YES then use this randomisation.

For all other recruitment phases:

1. Simulate stratified block randomisation for this phase within country and level of facility
2. Combine this simulation with prior actual randomisations
3. Check that combined randomisation has percent SOC between [48% - 52%]
4. If NO, then repeat steps 1-3. If YES proceed to next check.
5. Check that combined randomisation has balance within level of care between [45% - 55%]
6. If NO, then repeat steps 1-5. If YES then use this randomisation.

6.4. Trial intervention

The intervention arm to which each participating site is randomised will be offered to all eligible surgical patients for the duration of the trial.

Intervention arm

Participating sites which have been randomised to increased surveillance will need to provide increased surveillance to surgical patients with a predicted increased

postoperative risk as determined by the ASOS Surgical Risk Calculator⁹ stratification tool (also available at www.asos.org.za). Increased postoperative surveillance can include any of the following; i) admission to a higher care ward than had been planned at the time of surgery, ii) an increase in the frequency of nursing observations in the postoperative period, iii) ensuring that the patient is assigned to a bed in view of the nursing station, and not in a remote location in the postoperative ward, or iv) allowing family members to stay with the patient in the ward in the postoperative period. The nature of the offered increased postoperative surveillance will be left to the discretion of the healthcare workers and the participating sites. However, all sites will be encouraged to include more than one of the increased postoperative surveillance intervention. The healthcare providers will also receive information on the leading causes of postoperative mortality in African surgical patients as documented in ASOS; surgical site infections, bloodstream infection and acute respiratory distress syndrome, pneumonia, acute kidney injury, postoperative bleeding, and cardiac arrest.⁸ This will be known as the 'Postoperative surveillance bedside guide' and will be placed at the bedside of every patient flagged as high-risk by the ASOS Surgical Risk Calculator.⁹ This should be placed in a visible position at the patient's bedside e.g. posted on the wall above the patient's bed.

Control arm

Participating sites randomised to the control arm will provide usual postoperative care to patients. The care will be left to the discretion of the healthcare providers.

6.5. Data collection and collation

Dataset

This is a pragmatic trial in a resource-limited environment. As a result, a realistic data set will be fundamental to the success of the trial. We are confident that the proposed data set will achieve this objective, as it is smaller than the data sets used in ASOS,⁸ the European Surgical Outcomes Study (EuSOS),³ and the International Surgical Outcomes Study (ISOS),¹⁰ and these studies successfully achieved follow up on >95% of patients despite requiring data on all surgical patients at each participating centre for a week of surgery. We believe that these key data points will encourage centres to participate as there will not be an excessive burden of data collection.

Centre-specific data will be collected once for each hospital including: university or non-university hospital, number of hospital beds, number of operating rooms, number and level of critical care beds and details about the reimbursement status of the hospital.

An ASOS-2 case record form (CRF) will be completed for every eligible patient who undergoes surgery during the trial (appendix 3). Patients will be followed up until hospital discharge. This will be censored at thirty days i.e. patients will be followed up until discharge or for thirty days whichever is the shorter period.

6.6. Predefined protocol violation

A protocol violation will be defined as patients who were randomised to increased surveillance, but did not get any of the planned increased postoperative surveillance interventions.

6.7. Follow up procedures

Follow-up data will be collected by a site trial investigator. Investigators will review a participant's in-hospital medical records (paper or electronic) up to hospital discharge.

6.8. Schedule of assessment

Event/ visit	Screening	Pre-op	Daily postop	Hospital discharge
Inclusion/ exclusion criteria	X			
Demographic information		X		
Medical history		X		
Preoperative risk stratification, using the ASOS Surgical Risk Calculator ⁹		X		
Review of postoperative surveillance			X	X
Outcome assessment				X
End of trial form				X

7. Statistical considerations

7.1. Sample size calculation

This is a cluster randomised trial of hospitals in Africa. We will match hospitals on expected surgical volume in a week of surgery. This varied tremendously across the ASOS group; with a median number of surgical procedures per hospital for the study week in ASOS of 29 (IQR 10-71).⁸ The variability of the individual patient outcomes explained by the cluster (or surgical site) is taken into account in these sample size calculations. The intra-cluster correlation coefficient (ICC) in ASOS was 0.01. For the sample size calculation, we have therefore used a conservative ICC of 0.015.

Based on ASOS, we estimate the coefficient of variance for a 4-week recruitment period to be 0.63. A 4-week recruitment period is defined as the following; i) hospitals stop recruiting at the end of the week in which they have exceeded 100 enrolled patients, and ii) if a site had not reached 100 enrolled patients after 4 weeks of recruiting, it would stop recruiting.

The incidence of mortality in ASOS was 2.1%.⁸ We expect a 25% relative risk reduction in mortality through increased surveillance of postoperative surgical patients at high-risk of severe complications or in-hospital mortality. Based on the intra-cluster correlation coefficient (ICC) for the composite of severe complications and mortality in ASOS-2 of 1.5%, a coefficient of variance of 0.63, and stratification for the level of the surgical facility, and the volume of procedures per week, a trial for efficacy of increased postoperative surveillance would require 64,200 patients, from 642 surgical centres across Africa (Table 1).⁸ Based on a relative risk reduction of 25% in the intervention arm, the sample sizes for the primary outcome are shown in Table 1.

TABLE 1: Sample size calculations for the ASOS-2 Trial based on a power of 80%, 2-sided $\alpha = 0.05$ and a mean cluster size of 100 patients

Primary outcome (in-hospital all-cause mortality)					
Control event rate	Intervention arm	Relative risk	Intra-cluster correlation coefficient (ICC)	Coefficient of variance (CV)	Total clusters
2.0%	1.5%	0.75	0.015	0	536
2.0%	1.5%	0.75	0.015	0.63	664
2.0%	1.6%	0.80	0.015	0.63	1068

During the trial an external auditor ([name]) will check the event rate in the control arm of the study once 80% of all recruited patients have been captured on REDCap (practically this will take place around September 2019). The external auditor will use the event rate in the control arm to decide whether recruitment should continue beyond the target of 664 hospitals, and for how many months recruitment should continue. This specified interim analysis of data will not lead to adjustment of the prespecified alpha of 0.05.

7.2. Statistical analysis

Outcomes will be presented at a continental level. All institutional level data will be anonymised prior to publication. Categorical variables will be described as proportions and will be compared using chi-square tests. Continuous variables will be described as mean and standard deviation if normally distributed or median and inter-quartile range if not normally distributed. Comparisons of continuous variables between groups will be performed using t-tests, one-way ANOVA or equivalent non-parametric tests as appropriate.

The primary outcome will be in hospital mortality. Overall differences in in-hospital mortality will be compared between the intervention and control clusters. All analyses will account for clusters. A list of baseline risk factors (the risk factors in the ASOS Surgical Risk Calculator) will be included in the analysis. We will use logistic regression model to estimate the effect of increased postoperative surveillance, on the primary and secondary outcomes. We will calculate the odds ratios and their associated 95% confidence intervals. We will infer statistical significance if the computed 2-sided p-value is < 0.05 . A single final analysis is planned at the end of the study.

The detailed statistical analysis plan was added on 19 March 2020 and is attached as Appendix 6 to this document.

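### Section 7.2 names tests that assume independent patients, against its own clustering rule; at the plan's outcome ICCs an unadjusted 5% test would reject about 20–26% of true nulls

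*Combined protocol and SAP*

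**What the plan says.** The opening paragraph of section 7.2 gives general rules for comparing variables: "Categorical variables will be described as proportions and will be compared using chi-square tests", and "Comparisons of continuous variables between groups will be performed using t-tests, one-way ANOVA or equivalent non-parametric tests as appropriate". No clustered version of any of these tests is described. The next paragraph adds the general rule "All analyses will account for clusters", names logistic regression for the primary and secondary outcomes, and sets the threshold: "We will infer statistical significance if the computed 2-sided p-value is < 0.05".

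Appendix 6 (the SAP), section 3.2.1, analyses in-hospital death and the composite by GEE with a log link, clustering on hospitals nested in countries. Section 3.2.2 carries the same model to the sensitivity and subgroup analyses. Appendix 6 does not mention the chi-square, t-test or ANOVA sentences. It gives no method for comparing baseline characteristics, care received, single complications or days in hospital.

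**The concern.** A chi-square test or two-sample t-test on patient records treats every patient as an independent observation. Here the hospital was allocated, and patients from one hospital resemble each other to some degree. The standard error from such a test is then too small by the square root of the design effect, and its p-value is too small.

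An analyst who follows the opening paragraph of section 7.2 literally breaks the rule in the next paragraph. One who follows that rule has no named method for these variables. Two practical results are possible. Chance differences in patient characteristics could be marked significant and cast doubt on a sound randomisation. Differences in care received, or in single complications if these are compared, could look firmer than they are. Section 7.3 foresees at least one such comparison: it expects the CRF to show how the experience of patients who are not high-risk differs between the arms, and no method is given for it.

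**Working it through.** **Inputs.** All come from protocol section 7.1 unless noted.

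- Two-sided alpha 0.05 and 80% power: the Table 1 caption, "Sample size calculations for the ASOS-2 Trial based on a power of 80%, 2-sided", and the threshold in section 7.2.
- Mean cluster size m = 100 (Table 1 caption); CV of cluster size 0.63.
- ICC 0.015 for planning ("we have therefore used a conservative ICC of 0.015"), against 0.01 reported from ASOS.
- Main row of Table 1: "2.0% 1.5% 0.75 0.015 0.63 664".

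**Step 1: reproduce the plan's figure.** Design effect DE = 1 + [(1 + CV²)m − 1] × ICC.

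- CV 0: 1 + 99 × 0.015 = 2.485.
- CV 0.63: 1 + (139.69 − 1) × 0.015 = 3.080.

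Patients per arm before clustering, n = (1.960 + 0.842)² × [p₁(1 − p₁) + p₂(1 − p₂)] / (p₁ − p₂)²:

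- 2.0% v 1.5%: 7.849 × 0.034375 / 0.000025 = 10,792.
- 2.0% v 1.6%: 7.849 × 0.035344 / 0.000016 = 17,338.

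Clusters per arm = n × DE / 100 = 268.2, 332.4 and 534.1 for the three rows. Rounded up and doubled, these give 538, 666 and 1,070. Rounded down and doubled, they give 536, 664 and 1,068, exactly as in Table 1. The sample size therefore already rests on this design effect.

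**Step 2: error of an unadjusted test between arms.** Under the null the unadjusted statistic has variance DE rather than 1, so the rejection rate is 2 × [1 − Φ(1.96/√DE)].

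- ICC 0.015: 1.96/√3.080 = 1.96/1.755 = 1.117, giving 26.4%.
- ICC 0.01: DE = 1 + 138.69 × 0.01 = 2.387; 1.96/1.545 = 1.269, giving 20.5%.

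**Step 3: check by simulation.** Beta-binomial outcomes were generated for 664 clusters with a 2% event rate and no treatment effect, 4,000 runs each. With CV 0.63 the unadjusted test rejected in 27.3% (ICC 0.015) and 21.6% (ICC 0.01) of runs. With equal clusters it rejected in 20.1% and 15.3%.

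**Step 4: dependence on the ICC.** Only 0.01 and 0.015 stand in the documents; the other rows are assumptions.

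| ICC | DE, CV 0.63 | Rejects | DE, CV 0 | Rejects |
|---|---|---|---|---|
| 0.001 | 1.139 | 6.6% | 1.099 | 6.2% |
| 0.005 | 1.693 | 13.2% | 1.495 | 10.9% |
| 0.01 | 2.387 | 20.5% | 1.990 | 16.5% |
| 0.015 | 3.080 | 26.4% | 2.485 | 21.4% |
| 0.02 | 3.774 | 31.3% | 2.980 | 25.6% |
| 0.05 | 7.934 | 48.7% | 5.950 | 42.2% |
| 0.10 | 14.869 | 61.1% | 10.900 | 55.3% |

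**Step 5: dependence on cluster size.** The daily surveillance items concern high-risk patients only, and the documents do not say how many each hospital will have. Assuming a mean of 20 with the same CV and ICC 0.015, DE = 1 + (27.94 − 1) × 0.015 = 1.404; 1.96/1.185 = 1.654, giving about 10%.

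**The case against.** The strongest reply is that the clustering rule is universal, stands in the same section and follows the list of tests. It can be read as governing them, since cluster-adjusted and cluster-summary forms of these tests exist. A reader might infer a firm plan to ignore clustering; the text does not support that. What remains is an internal inconsistency: the tests are named in their ordinary form and no clustered form is specified.

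A reader might also infer that 26% is a minimum. It is not. It uses an ICC that the protocol calls conservative, and the ASOS value gives about 20%. Both ICCs relate to outcomes: section 7.1 attaches 1.5% to the composite, and Table 1 uses it for mortality. Case-mix and process variables may cluster more or less, but the documents give no ICC for them. The formula also leaves out the stratification by country and facility level in section 6.3. Between-hospital variation explained by those factors is largely balanced across arms, which lowers the true rate.

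The exposure is limited as well. Appendix 6 closes its list of prespecified analyses without any between-arm test of single complications or length of stay, and no prespecified decision depends on a baseline p-value. Its per-protocol and patient-level analyses are set out separately and do not rely on the section 7.2 tests. Facts recorded once per hospital, such as bed numbers or university status, have no within-hospital correlation to ignore.

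These points narrow the concern but do not remove it. Section 7.2 is still the only written method for comparing other patient-level variables, and it conflicts with its own rule.

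**Conclusion.** The inconsistency is real and should be corrected. It concerns descriptive, baseline and process comparisons of patient-level data between arms. The size is a false-positive rate of about 20% to 26% at a nominal 5%, on three assumptions: the variable shares the outcome ICC of 0.01 to 0.015, clusters average 100 patients with CV 0.63, and stratification explains none of the between-hospital variation. Relaxing either of the last two in the likely direction lowers the figure; a higher ICC would raise it, but none is documented.

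A reader might conclude that the trial's main result carries this error. It does not: the effect estimates for death and for the composite come from a model that accounts for hospitals within countries.

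**What to change.** Replace the two test sentences in section 7.2, keeping the descriptive summaries (proportions, mean and SD, median and IQR), with:

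> Baseline patient and hospital characteristics will be summarised by arm without significance tests. Any between-arm p-value or confidence interval on patient-level data will use a method that accounts for clustering as in Appendix 6 (hospitals within countries), for example GEE, or a cluster-summary or cluster-adjusted rank method for skewed variables.

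Repeat the second sentence in Appendix 6 so that the two documents agree. This keeps the SAP's nesting and an option for skewed data. The cost is small: a wording change, no new data, and no change to the sample size or the main analyses. Intervals for these secondary comparisons will be wider than unadjusted ones by √DE, about 1.5 to 1.8 times at the plan's own values and less where clustering is weaker.
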